4.2.6 Dosing-regimen

A FTU corresponding to 0.5 g of MC2-25 cream, or MC2-25 vehicle is to be applied on the vulvar region (i.e., the clitoris and periclitoral skin, interlabial sulci, labia minora, posterior fourchette and perineum, anal and perianal skin) after each toilet visit (during day and night) starting on the day of the Baseline visit. This dosing regimen has been chosen to ensure replenishment of Ala-Gln on the vulvar region (as the cream will likely be removed due to wiping after urination) and to counteract any increase in urea concentration e.g., due to insufficient cleaning/wiping of urine residues after toilet visits. This will also counteract any increase in urea due to urinary leakage between toilet visits. Limited information is available on the normal range of urination frequencies in women. However, a recent survey investigating urination frequencies in 2534 healthy women reported reference ranges for urination frequencies between 2-10 times/day and 0-4 times/night (Wyman et al., 2022). Consequently, the maximum number of applications will be 12 per day. Assuming up to

12 toilet visits per day leads to a maximum total daily dose of 6.0 g of MC2-25 cream (3%) corresponding to 0.18 g Ala-Gln per day or 17 mg MC2-25 cream per cm² skin per day (assuming that 6.0 g cream per day will be distributed on a skin area corresponding to two handprints or 358 cm²).

Systemic safety margin for Ala-Gln: Ala-Gln in the form of Dipeptiven® can safely be administered intravenously up to a maximum daily dose of 0.5 g Ala-Gln/kg/day. Under the assumption that an average adult woman weighs around 70 kg this corresponds to a maximum IV dose of 35 g Ala-Gln per day. If all Ala-Gln applied per day as MC2-25 cream was to penetrate into the systemic circulation this would correspond to a systemic safety margin of approximately 200. However, less than 1% of the topically applied Ala-Gln dose was recovered in the receptor fluid (a surrogate for absorption into the systemic circulation) in an in vitro whole human skin penetration trial with Ala-Gln cream (see IB Section 4.3.1.2) which would correspond to a systemic safety margin of approximately 20,000. Whether whole human skin penetration data can be extrapolated to VLS or not can be debated as VLS skin could be argued both to be a deficient or an efficient skin barrier.

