6.1.2 Dosing and administration

MC2-25 cream, or MC2-25 vehicle must be applied after each toilet visit following urination (during day and night) starting on the day of the Baseline visit. The MC2-25 cream, or MC2-25 vehicle should be applied by the patient in a thin saturating layer to the vulvar region (i.e., vulvar region includes clitoris and periclitoral skin, interlabial sulci, labia minora, posterior fourchette and perineum, anal and perianal skin). Approximately one fingertip-unit (FTU), roughly corresponding to 0.5 g cream is to be used after each toilet visit (during night and day). The vulvar region may be gently cleaned with water and dabbed dry with toilet paper or a clean cloth before each application of the trial treatment. Assuming, a maximum of 12 toilet visits are needed over a period of 24 hours, the maximum daily dose is expected to be around 6.0 g. A treatment application manual will be available for patients.

Reference is made to Section 4.2 for the rationale behind the dosing-regimen.

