### **2.4.3 Drug Accountability, Extent of Exposure and Study Treatment Compliance**

Patients will at visit 6, visit 8 and visit 10 be asked to return the dispensed carton box with the used and unused tubes. All returned boxes with used and unused tubes will be weighed together to determine the amount of IMP used. The calculations for drug used will use: a) a carton box packed with 8 full labelled tubes weighs on average 658.112 g; b) a full labelled tube weighs on average 73.928 g.

The *amount of drug used* in grams is derived as the sum of the difference in drug weight dispensed and returned by kit; when there are tubes missing, assuming all missing tubes were fully used. This principle will be used to calculate the *total amount of drug used*.

The *duration of study treatment* is derived as the time in days from the date of first study drug application to the date of last study drug application. Per day, the number of toilet visits and the number of study drug applications are reported in a subject diary. If diary data is coming from separate diaries on the same day, it will be pooled to obtain the total number of toilet visits for that given day. *Compliant days* are days, where the number of toilet visits does not exceed the number of study drug applications by more than one. *Non-compliant days* are days of the treatment period, where the number of study drug applications is lower than the number of toilet visits minus 1, where the number of study drug applications or the number of toilet visits is missing, and where no diary entry is given. *Overall compliance (%)* is 100 times the number of compliant days divided by the duration of study treatment in days. Treatment compliance will be categorized to less than 80% versus 80% or more and to less than 70% versus 70% or more.

Duration of study treatment, number of compliant and non-compliant days, overall compliance, total amount of drug used, and weekly amount of drug used will be presented by summary tables by treatment group.

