#### 4.2.5 Per-Protocol Set (PPS)

A subset of the MFAS patients who completed the trial with WI-NRS data for Week 12 and are deemed to have no important protocol deviations that could interfere with the objectives of this trial. Important deviations of eligibility criteria and other deviations from the protocol will be assessed. Important deviations from the protocol may lead to exclusion of a patient or data points from the PPS, which could have interfered with the administration of the treatment or the evaluation of treatment effect. All such decisions will be identified and documented before the final trial database is unblinded. Important protocol deviations may include, but are not limited to, randomized treatment not taken, medication non-compliance (<80%), missing 3 or more consecutive application days, and intake of prohibited concomitant therapies, which may have an impact on the primary endpoint.

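### SAP 2.4.3 forgives one missed application a day however many are due, so overall compliance depends on toilet frequency and can rank patients opposite to the share of doses they applied

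*SAP*

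**What the plan says.** Protocol 6.1.2 states that cream or vehicle "must be applied after each toilet visit following urination (during day and night) starting on the day of the Baseline visit". The number due is therefore the patient's own number of visits. Protocol 4.2.6 cites "reference ranges for urination frequencies between 2-10 times/day and 0-4 times/night" from a survey of healthy women and plans for at most 12 applications a day.

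SAP 2.4.3 derives compliance from the application diary, which records both counts. A day is compliant "where the number of toilet visits does not exceed the number of study drug applications by more than one". It is non-compliant "where the number of study drug applications is lower than the number of toilet visits minus 1", and also when either count is missing or there is no diary entry. Overall compliance "is 100 times the number of compliant days divided by the duration of study treatment in days". The same section adds: "Treatment compliance will be categorized to less than 80% versus 80% or more and to less than 70% versus 70% or more".

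SAP 4.2.5 gives as examples of important deviations "medication non-compliance (<80%), missing 3 or more consecutive application days", and says: "Important deviations from the protocol may lead to exclusion of a patient or data points from the PPS". It does not state that its 80% refers to the percentage in SAP 2.4.3. That is, however, the only compliance percentage the SAP defines, and it uses the same cut.

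**The concern.** The tolerance is an absolute number, one application, while the amount due varies several-fold between women. One miss is half the dose at 2 visits a day, a quarter at 4 and about 8% at 12. The same score therefore sets a different standard of adherence for each woman, lax for those with few visits and strict for those with many.

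Two outputs depend on the score. One is the compliance summary by arm. The other is the below-80% flag, which can lead to exclusion from the per-protocol set (PPS). The PPS is sensitivity analysis (c) for WI-NRS in SAP 5.5.1 and is used in the same way for WP-NRS and the Skindex-29 domains (SAP 5.5.2 and Table 5). A PPS is meant to hold patients who took the treatment adequately. This flag can pass a patient who did not and catch one who did.

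**Working it through.** The plan gives no figure of its own to reproduce here, so the check applies its rule directly.

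**Inputs.** Compliant-day rule, overall compliance and the 80% cut: SAP 2.4.3 and 4.2.5. One application due per toilet visit: Protocol 6.1.2. Visits per 24 hours: 2 + 0 = 2 up to 10 + 4 = 14, with 12 as the planned maximum of applications (Protocol 4.2.6). Treatment length: 84 days, taken from the nominal 12 weeks.

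**Step 1: constant pattern.** Let V be visits and A applications on a day. The day is compliant if V − A ≤ 1. The score is 100 × compliant days / 84; the share applied is 100 × A/V.

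| Daily pattern | V − A | Compliant days | SAP score | Share applied |
|---|---|---|---|---|
| 1 of 2 | 1 | 84/84 | 100% | 50.0% |
| 3 of 4 | 1 | 84/84 | 100% | 75.0% |
| 8 of 10 | 2 | 0/84 | 0% | 80.0% |
| 10 of 12 | 2 | 0/84 | 0% | 83.3% |

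The order by score is the reverse of the order by share applied.

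**Step 2: random misses.** Suppose each due application is made independently with probability a. Then P(compliant day) = P(Binomial(V, 1 − a) ≤ 1). A score of at least 80% needs 68 of 84 days (68/84 = 81.0%; 67/84 = 79.8%), so P(score ≥ 80%) = P(Binomial(84, P(compliant day)) ≥ 68).

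For example, at a = 0.90 and V = 8: 0.9^8 + 8 × 0.1 × 0.9^7 = 0.430 + 0.383 = 0.813 per day, which gives 60% for reaching 68 days.

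| V | P(compliant day), a = 0.90 | P(score ≥ 80%), a = 0.90 | P(score ≥ 80%), a = 0.95 |
|---|---|---|---|
| 4 | 0.948 | >99.9% | >99.9% |
| 6 | 0.886 | 99% | >99.9% |
| 8 | 0.813 | 60% | >99.9% |
| 10 | 0.736 | 8% | 99.9% |
| 12 | 0.659 | 0.2% | 98% |

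At the low end, a = 0.60 and V = 2 gives a daily probability of 1 − 0.4² = 0.84, and an 82% chance of scoring at least 80%.

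**Step 3: the adherence that the 80% cut demands.** Solving P(compliant day) = 0.80 for a gives 55% at 2 visits, 79% at 4, 86% at 6, 90% at 8 and 93% at 12.

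**Step 4: a proportional measure.** Applications divided by visits gives 75.0% for 3 of 4 (below 80%) and 83.3% for 10 of 12 (above 80%). Both classifications reverse, and the order matches the doses applied.

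**The case against.** The strongest reply is that little hangs on this. The primary analysis is treatment policy on the full analysis set with multiple imputation, and compliance does not enter it. The PPS is one of four sensitivity analyses, the binary secondary endpoints have no PPS analysis, and no success rule depends on it. Under-dosing is also visible elsewhere: grams used are tabulated by arm, Protocol 9.4.7.1 adds the number of applications, and Listings 16.2.5.6 and 16.2.5.7 show diary and compliance data by patient. All of this stands and limits the consequence. None of it corrects the percentage or the flag.

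A second reply is that one forgiven visit is a sensible allowance. Dosing follows urination while the diary counts toilet visits, so the margin could absorb other visits or counting error. That may be so, but the SAP gives no rationale, and such an allowance should grow with the number of visits. The 80% cut already provides slack.

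Third, the constant patterns are extremes. That is also fair: at 95% adherence the rule does little harm at any frequency tabulated.

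Three stronger readings are tempting, and the documents do not support them.

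- *That a score below 80% removes the patient.* SAP 4.2.5 makes exclusion possible, not automatic, and SAP 3.5 sends deviations to a minuted blind review. That review could keep a woman applying 10 of 12 doses.
- *That the rule removes the women most exposed to urine.* The exposure argument in Protocol 4.2.5 rests on leakage. Protocol 4.2.6 also mentions residue after toilet visits, but neither section treats visit frequency as a measure of exposure.
- *That the PPS is materially changed or no longer informative.* The documents give no distribution of visits or adherence in this population, so no expected number of misclassified patients can be derived, and no difference between arms is shown.

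**Conclusion.** The point holds as a defect in a stated derivation: the SAP 2.4.3 percentage is not comparable between women with different toilet frequencies and can reverse their order. The constant-pattern results follow from the rule alone. The probabilities rest on independent misses, a constant visit count and 84 diary days; clustered misses would change them. The problem arises mainly at intermediate adherence with frequent visits, or low adherence with few.

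The link to the PPS rests on reading the 80% in SAP 4.2.5 as the SAP 2.4.3 percentage, which is the natural reading but is not stated. The reach is the compliance tables and the PPS analyses of WI-NRS, WP-NRS and Skindex-29. How many of the 33 patients are affected, and in which direction the PPS estimate would move, cannot be known from the documents. The change should be made, but the primary result does not depend on it.

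**What to change.** In SAP 2.4.3, define overall compliance (%) as 100 × Σ min(applications, toilet visits) / Σ toilet visits, summed over the days of treatment. The daily cap stops extra applications on one day from offsetting misses on another. Count a day with a missing count or no diary entry as zero applications at the patient's own mean visit count. Apply the 70% and 80% categories to this percentage. In SAP 4.2.5, cross-refer explicitly to SAP 2.4.3 for the below-80% criterion. Keep the compliant-day count as a descriptive row.

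The cost is SAP wording and a few lines of derivation code before unblinding. The diary already collects both counts, and the protocol sets no numerical compliance threshold (Protocol 6.4 and 9.3), so the protocol text need not change. The small downside is the assumed visit count on days without complete entries, which the SAP should state.

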### **2.4.4 Concomitant Medication and Non-Drug Therapies**

All medications and treatments (i.e., prescription drugs [including COVID-19 vaccination programs], over the counter [OTC] drugs and vitamins, herbal and dietary supplements, and lubricants used with sex), hereafter referred to as therapies, taken within 30 days prior to screening or during the trial will be recorded. Information about the total daily dose, route of administration, start and discontinuation dates, and indication are to be recorded in the eCRF.

All verbatim terms of drug and non-drug therapies will be encoded according to the WHO Drug Dictionary in its latest annual version and classified by primary Anatomic Therapeutic Chemical (ATC) class level 2 and PT.

A therapy or procedure is *prior* if starting and ending before or at the Baseline visit (Day 0). A therapy or procedure is *prior ongoing* if starting before or at the Baseline visit (Day 0) and ending after the Baseline

visit (Day 0) or ongoing at study completion. A therapy or procedure is *concomitant*, if starting at or after the Baseline visit and ending after the Baseline visit (Day 0) or ongoing at study completion.

Frequency counts and percentages of patients with at least one prior, prior ongoing, or concomitant therapy will be presented in separate summary tables by ATC level 2 and 4, PT, treatment group and overall, respectively.

## 2.5 Baseline Characteristics

### 2.5.1 Disease Characteristics

All patients are suffering from vulvar lichen sclerosus. At screening and/or at randomisation, the trial population is described by

- VLS History (diagnosis and symptoms (year, who made diagnosis, biopsy (y/n), family members with VLS, regular VLS treating physician visits, type of treating physician) at Screening 1 visit.
- In-clinic values for Worst Itch Numeric Rating Score (WI-NRS), Worst Pain Numeric Rating Score (WP-NRS), and Worst Penetrative sex related Pain Numeric Rating Score (WPP-NRS) at Screening 1 and Baseline visits; weekly diary means for Worst Itch Numeric Rating Score (WI-NRS), Worst Pain Numeric Rating Score (WP-NRS) at Baseline visit
- Vulvar lichen sclerosus Area and Sign Severity Index (VASSI) at Screening 1 and Baseline visits
- Clinician's Global Assessment of VLS (CGA) at Screening 1 and Baseline visits
- Menopausal status at Baseline visit
- International Consultation on Incontinence Questionnaire Urinary Incontinence Short Form (ICIQ-UI-SF) at Baseline visit
- The Vulvar Quality of Life Index (VQLI) at Baseline visit
- Skin specific multidimensional quality-of-life (Skindex-29) at Baseline visit

Baseline disease characteristics will be presented by summary tables by treatment group and overall.

### 2.5.2 Demographics

At Screening, age, ethnic origin (Hispanic or Latino, or not), and race (White, Black or African America, Native Hawaiian or Other Pacific Islander, Asian, American Indian or Alaska Native, or Other) will be recorded.

Demographics will be presented by summary tables by treatment group, and overall, for the following populations: Full Analysis Set, Modified Full Analysis Set, Safety Analysis Set, and Per-Protocol Set.

### 2.5.3 Medical and Surgical History

Entries of medical and surgical history, including medical diagnoses and surgical procedures, are recorded with start and end times, as well as ongoing status, at the Screening 1 visit. Verbatim terms of diagnoses and surgeries will be coded according to MedDRA version 27.0 classified according to primary SOCs and PTs. Frequency counts and percentages of patients with at least one entry in the medical and surgical history and/or at least one concurrent diagnosis will be presented in summary tables by primary SOC, PT, treatment group, and overall. An entry in the medical history is a concurrent diagnosis if ongoing at the Screening 1 visit.

### 2.5.4 Prior, Prior Ongoing, and Concomitant Medication

A therapy or procedure is *prior* if starting and ending before or at the Baseline visit (Day 0). A therapy or procedure is *prior ongoing* if starting before or at the Baseline visit (Day 0) and ending after the Baseline

visit (Day 0) or ongoing at study completion. A therapy or procedure is *concomitant*, if starting at or after the Baseline visit and ending after the Baseline visit (Day 0) or ongoing at study completion.

Frequency counts and percentages of patients with at least one prior, prior ongoing, or concomitant therapy will be presented by summary tables by ATC level 2 and 4, PT, treatment group, and overall.

## 2.5.5 Vital Signs at Baseline

Systolic and diastolic blood pressure, heart rate, and body temperature at Week 0, as well as height and weight from demographics at the Screening 1 visit, along with body mass index, derived as weight in kg divided by the square of height in meters, will be presented in summary tables by treatment group, and overall.

## 2.5.6 Physical Examination at Baseline

A complete physical examination (including all body systems as well as the vulvar region) is required at Screening 1; the body systems are as follows:

- vulva region
- general appearance
- dermatological,
- thyroid,
- head, neck, throat
- heart / lungs
- abdomen
- lymph nodes
- musculoskeletal
- cardiovascular
- neurological

In each case, both abnormality and clinically significant status will be reported; these will be combined to create three categories: normal, abnormal/non-clinically significant, and abnormal/clinically significant. These will be presented in summary tables (frequency counts and percentages) by treatment group, and overall.

## 3 General Specifications for Analysis

### 3.1 Analysis Software

All analyzes will be carried out on the Statistical Analysis System (SAS®) Analytics Pro, version 9.4 including statistical procedures in the SAS/STAT® version 14.1 module [9].

### 3.2 Descriptive Statistics

All endpoints will be summarized using summary statistics for each treatment group, by visit, where appropriate.

#### 3.2.1 Summarizing Categorical Data

Categorical including binary data will be summarized by frequency counts and percentages. The denominator of the percentages will be indicated if ambiguous. All categories will be displayed in summary tables including those with zero counts. A category of missing counts will be added. Per post-baseline visit,

summaries of secondary endpoints of improvement will also include p-values of exact binomial tests on improvement rates within each treatment group.

### 3.2.2 Summarizing Continuous Data

Continuous data including scores will be summarized by arithmetic mean, standard deviation (SD), median, quartiles, and ranges. Quartiles are given as (*lower quartile, upper quartile*) and ranges as (*minimum, maximum*). The number of non-missing values will also be displayed. Per post-baseline visit, summaries of changes from baseline in primary and secondary endpoints, on WI-NRS and WP-NRS, will also include p-values of t-tests on the change within each treatment group.

## 3.3 Disposition of Patients

A patient is regarded as *screened* if they have signed informed consent and carried out any of the assessments at the Screening visit 1. A patient who fulfils the trial eligibility requirements (Visit 1 and the Baseline Visit) will be *randomised*, i.e., randomly assigned to treatment with IMP and given a randomisation number. A screened patient who either did not fulfill the inclusion and exclusion criteria, or withdrew from the trial before randomisation, is defined as a *screen failure*.

Patient disposition will be summarized by the number (frequency counts and percentages) of patients

- screened
- failed screening
- randomised
- started IMP treatment
- prematurely discontinued IMP treatment
- completed IMP treatment
- prematurely withdrawn from trial
- completed trial

Patient disposition will be summarized by treatment group and overall.

## 3.4 Premature Discontinuation of Treatment and/or Study Participation

On patient disposition (see Section 3.3) counts and percentages will also be given by reason for screen failure and premature discontinuation of IMP treatment and/or withdrawal from trial.

## 3.5 Protocol Deviations

Important protocol deviations may include, but are not limited to, IMP non-compliance, missing consecutive application days, and intake of prohibited concomitant therapies, which may have an impact on the primary endpoint. Important deviations related to study inclusion or exclusion criteria, conduct of the trial, or patient assessment, will also be reported.

All observed protocol deviations will be listed. Protocol deviations will be classified as major or minor in a minuted meeting for blind review of the database conducted prior to final database lock and unblinding. All protocol deviations and major protocol deviations will be presented in frequency tables.

## 4 Study Specifications for Analysis

### 4.1 Interim Analysis

The current trial is a phase 2 trial and is powered to detect statistical significance on the primary endpoint and to inform further clinical development. The expected recruitment period is relatively short, and the double-blind treatment period is only 12 weeks. Thus, no interim analysis is planned.

